Study Protocol

Official Title: Simple Non-invasive Breathing Device to Improve Pulmonary Flow Pusability in Single Ventricle Post Fontan

ClinicalTrials.gov ID (NCT number): STUDY22050151

Protocol Date: 1/1/24

Scientific Background

By replicating biphasic ventilation's benefits, Sniff-PEP breathing may prove to improve outcomes in Fontan patients. This research will furnish preliminary data encompassing CMR, biomarker studies, and QoL analyses on Sniff-PEP breathing's effects. With our multidisciplinary team's expertise, we are well-equipped to evaluate this promising intervention, laying the groundwork for broader, multi-institutional research endeavors.

Study Objectives

A. Specific Aims

Aim #1: To evaluate the acute effects of oPEP in Fontan patients undergoing clinically indicated echocardiogram

Hypothesis: oPEP use in Fontan patients will increase flow pulsatility in the inferior vena cava, hepatic veins, Fontan circuit and pulmonary arteries that will ultimately lead to increased cardiac output

Aim #2: To evaluate the effects of one month use oPEP in Fontan patients undergoing clinically indicated echocardiogram

Hypothesis: oPEP use in Fontan patients for a month will increase flow pulsatility in the inferior vena cava, hepatic veins, Fontan circuit and pulmonary arteries that will ultimately lead to increased cardiac output

Study Design & Methods

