[name] will be screening pediatric cardiology patients who will be having their appointments in the Lawrenceville locations. Of those patients who meet inclusion criteria, either he, [name], or another appointed official will approach the patient and/or their guardians and discuss the study with them and provide them information. If they agree to participate in the study, then a demonstration will be done for the subject on how to use the device appropriately. The subject will be given their own personal device and will practice the breathing technique for the device. This device has been catalogued, never been used by another person, and sanitized. The patient will place the device between their lips and create a tight seal. Then, they will start by inhaling through their nose and exhaling through their mouth through the device. The subject will practice till they feel comfortable with the breathing maneuver. An initial research quality of life questionnaire will be given to the subject and their guardians for completion. Subject then will have his standard clinic echocardiogram. After completion of the standard echocardiogram protocol, the subject will perform the breathing exercise through the device. While breathing through the device, we will obtain echocardiogram measurements as detailed below:

- a. Subcostal sagittal
- i. Color Doppler of IVC and hepatic veins
- ii. Pulse wave Doppler of IVC (distal to hepatic veins)
- iii. Pulse wave Doppler of hepatic vein

- b. Apical view
- i. 2D of systemic outflow tract
- ii. Color Doppler of systemic outflow tract
- iii. Pulse wave Doppler of systemic outflow tract Doppler
- iv. Continuous wave Doppler of neoaortic valve

- c. Suprasternal coronal Notch view
- i. If possible, 2D of SVC and RPA/LPA junction
- ii. Color Doppler of SVC and RPA/LPA junction
- iii. Pulse wave Doppler of SVC, RPA, and LPA

- d. (if LPA not well seen in suprasternal coronal) Suprasternal sagittal view
- i. Color Doppler of LPA
- ii. Pulse wave Doppler of LPA

These echo measurements will then be confirmed or read by a cardiologist who will be blinded against the condition the patient is in (normal breathing vs breathing through oPEP). 20% of the measurements will be confirmed by another reader.

The patient will complete a brief questionnaire at baseline. We will instruct the patient to use the device 3-4 times daily for a duration of 10-15 minutes. After a period of

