approximately 4 weeks, the patient will return to the Lawrenceville location and will have a repeat echocardiogram according to the protocol below:

- a. Subcostal sagittal
- iii. Color Doppler of IVC and hepatic veins
- iv. Pulse wave Doppler of IVC (distal to hepatic veins)
- v. Pulse wave Doppler of hepatic vein

- b. Apical view
- vi. 2D of systemic outflow tract
- vii. Color Doppler of systemic outflow tract
- viii. Pulse wave Doppler of systemic outflow tract Doppler
- ix. Continuous wave Doppler of neoaortic valve

- c. Suprasternal coronal Notch view
- x. If possible, 2D of SVC and RPA/LPA junction
- xi. Color Doppler of SVC and RPA/LPA junction
- xii. Pulse wave Doppler of SVC, RPA, and LPA

- d. (if LPA not well seen in suprasternal coronal) Suprasternal sagittal view
- xiii. Color Doppler of LPA
- xiv. Pulse wave Doppler of LPA

These echo measurements will again be confirmed or read by a cardiologist who will be blinded against the condition the patient is in (normal breathing vs breathing through oPEP). 20% of the measurements will be confirmed by another reader.

At this point, the subject and guardian will be given a follow up questionnaire and we will leave them with the device for their personal use if they choose to keep it.

Otherwise, we will accept the returned device, catalogue return, and will disposed in an appropriate manner.

Eligibility Criteria

Inclusion Criteria:

- Patients with single ventricle with Fontan palliation
- Over the age of 8 years who would be cooperative with breathing through the oPEP device

Exclusion Criteria:

- Patients with Fontan palliation under the age of 8 years
- Patients who have interrupted inferior vena cava

- Patients with abnormal pulmonary artery anatomy

Statistical Considerations

The pulmonary pulsatility index, hepatic vein and portal vein pulsatility index, aortic valve VTI will be compared before and at the time of using the oPEP device. A repeated t-test will be used for within subject comparison. Since this is a pilot study we will plan to include 15 patients.

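### The quality-of-life form comes before the echo at baseline but, on the natural reading, after it at 4 weeks, so a QoL change may include an effect of when in the visit the form was given

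*Combined protocol and SAP*

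**What the plan says.** The Combined protocol and SAP deals with questionnaires in three places under Study Design & Methods and with QoL as an output in one place in the Scientific Background.

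- **Baseline visit, before the echo.** After the demonstration comes practice: "The subject will practice till they feel comfortable with the breathing maneuver". Next: "An initial research quality of life questionnaire will be given to the subject and their guardians for completion". Next: "Subject then will have his standard clinic echocardiogram". The recordings made while breathing through the device follow the standard echo.
- **Baseline visit, after the echo and reading text.** A further sentence says "The patient will complete a brief questionnaire at baseline". It names the patient only, has no word fixing its place in the visit, and does not say whether this is the initial form again.
- **4-week visit.** The patient "will have a repeat echocardiogram according to the protocol below". The list of views and the blinded reading follow, and then "At this point, the subject and guardian will be given a follow up questionnaire". The same sentence goes on to the family keeping the device.
- **Scientific Background.** The study is to supply "preliminary data encompassing CMR, biomarker studies, and QoL analyses".

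Neither aim mentions QoL. Statistical Considerations covers pulsatility indices and aortic valve VTI, before and during device use, with a within-subject t-test in 15 patients. It describes no QoL comparison. No instrument or recall period is named.

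**The concern.** A before-and-after score is easiest to interpret when both measurements are taken under the same conditions. Here the baseline form is completed before that day's echo and the follow-up form, apparently, after it. Relief that the scan is over, fatigue, or a remark about the flow pattern could then affect the follow-up answers and not the baseline ones. The baseline form also comes after device practice, so it does not wholly precede contact with the device.

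The study has one group and is open to patients and guardians, so no comparison arm carries the same shift and cancels it. If a QoL change is reported from this pilot as groundwork for a larger study, part of it could reflect questionnaire position and not a month of use. Nothing in the data could separate the two afterwards.

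**Working it through.** **Step 1. Order of events, side by side.**

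| | Baseline | 4 weeks |
|---|---|---|
| Device handling before the form | Demonstration and practice | About 4 weeks of home use |
| QoL form before the echo | Yes, to subject and guardians | None described |
| Echo | Standard, then on device | Repeat echo |
| Form described after the echo | Brief questionnaire, patient only, timing not fixed | Follow-up questionnaire, to subject and guardian |

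**Step 2. Which pairs can be formed.**

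- *Guardian.* The only stated baseline is the pre-echo form, and the only follow-up is described after the echo. The positions differ.
- *Patient, if the brief questionnaire is the initial form restated.* Pre-echo against post-echo. The positions differ.
- *Patient, if the brief questionnaire is a separate post-echo form and is the one paired with follow-up.* Both come after an echo, so the order broadly matches, but this baseline is taken straight after the on-device recordings.

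No reading gives both respondents a matched position and a baseline free of prior device use.

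**Step 3. What a before-after change contains.** In one group with one fixed order:

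observed change = one-month change due to the device + position effect + time, expectation and other uncontrolled effects.

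The terms cannot be separated.

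**Step 4. Illustrative size.** The documents give no SD, effect size, alpha or QoL test, so there is no figure of the plan's own to reproduce. Apart from the 15 patients, every input is an assumption: 15 complete pairs, a two-sided 5% paired t-test, no true device effect, no time or expectation effect, and a pure position shift of d standard deviations of the paired change towards better scores.

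- Degrees of freedom: 15 − 1 = 14. Critical value: 2.145.
- Noncentrality: d × √15 = d × 3.873.
- Chance of a false improvement: P(T > 2.145), with T noncentral t on 14 degrees of freedom.

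| Assumed shift d | Noncentrality | Chance of false improvement |
|---|---|---|
| 0 | 0 | 2.5% |
| 0.05 | 0.194 | 3.8% |
| 0.1 | 0.387 | 5.5% |
| 0.2 | 0.775 | 10.8% |
| 0.3 | 1.162 | 19.0% |
| 0.5 | 1.936 | 43.8% |

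By symmetry, a shift of the same size towards worse scores, as fatigue might cause, gives the same chances of a false worsening and would tend to hide a real benefit.

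**The case against.** The strongest reply is that the text is less definite than the table in Step 1 suggests. The follow-up form is never called a QoL form; it could be the counterpart of the brief questionnaire or ask about experience with the device. The phrase that introduces it comes after a paragraph on blinded reading and second readers, so it may mean no more than at this visit. Both points stand, which is why the mismatch is the natural reading and not a certainty. Three things still favour that reading: an initial form implies a later one, both forms go to subject and guardian, and no other post-baseline questionnaire is described. If the follow-up is not the QoL form, the plan describes no way to measure QoL change. If its timing is loose, no common position is fixed and the same edit is needed.

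A second reply is that no planned analysis is affected. It is true that QoL is absent from the aims and from Statistical Considerations. What is exposed is the output promised in the Scientific Background, and that limits the weight of the point.

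A third reply is that a same-day echo may barely move the score, especially if the form asks about past weeks, and that expectation and time trends in an open single-group study are larger threats. This also stands. The 2.5% in the first row is not what matched timing would deliver in practice, because it assumes those other effects away.

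A reader might infer that any QoL change in this study is contaminated by the echo visit, or that the plan plainly sets mismatched timing and would report the result as the device's effect. The documents do not support either. They give no evidence that a position effect exists, leave the identity and timing of the forms partly open, and do not say how a QoL change would be reported.

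**Conclusion.** The point holds in a limited form. Followed as written, on the natural reading, the plan takes the QoL form before the echo at baseline and its apparent counterpart after the echo at 4 weeks. The mismatch is clearest for guardians; for patients it depends on what the brief questionnaire is. A QoL change may therefore include an effect of questionnaire position.

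The size and direction of that effect are unknown, and it may be nil. The range of 2.5% to 44% for a false improvement shows what 15 pairs would do under assumed shifts of 0 to 0.5 SD; it does not estimate the bias in this trial. The echo comparisons in Statistical Considerations are untouched. This is a cheap improvement to an exploratory output, worth making before enrolment because it cannot be repaired once the forms have been collected.

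**What to change.** In Study Design & Methods:

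1. **Baseline visit.** Give the QoL form to patient and guardian before the device demonstration. State whether the initial and the brief questionnaires are the same form. If they differ, say what the brief one is for and keep it out of the QoL change.
2. **4-week visit.** Name the follow-up form as the same QoL form. Give it to the same respondents on arrival, before the echo and before any result is discussed.
3. **Comparison.** Compare patient with patient and guardian with guardian. Name the instrument and its recall period.
4. **Statistical Considerations.** Add one sentence saying that QoL change will be summarised descriptively.

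The cost is some wording in two paragraphs, that added sentence, and a small change in visit flow, with no added visits, procedures or patients. Matching the position removes this one source of bias. It does not remove expectation or time effects, so any QoL change should still not be presented as a demonstrated effect of the device.

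### The analysis tests a portal vein index that is neither hypothesised nor listed for recording, and omits an IVC index for a site that is both

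*Combined protocol and SAP*

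**What the plan says.** Three parts of the protocol bear on this point.

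- **Study Objectives, Aims 1 and 2.** Both hypotheses name the same four sites. Device use "will increase flow pulsatility in the inferior vena cava, hepatic veins, Fontan circuit and pulmonary arteries", and this is expected to raise cardiac output.
- **Study Design & Methods, echo lists at baseline and at about 4 weeks.** The subcostal part of each list contains "Pulse wave Doppler of IVC (distal to hepatic veins") and a pulsed-wave Doppler of the hepatic vein. The suprasternal part contains "Pulse wave Doppler of SVC, RPA, and LPA". The apical part covers the systemic outflow tract and the neoaortic valve. The baseline list is tied to device use: "While breathing through the device, we will obtain echocardiogram measurements as detailed below".
- **Statistical Considerations.** After the pulmonary pulsatility index, the outcome sentence reads: "hepatic vein and portal vein pulsatility index, aortic valve VTI will be compared before and at the time of using the oPEP device". A within-subject t-test is planned in 15 patients, a number justified only by the study being a pilot.

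**The concern.** A paired test needs two values per patient, here one before and one during device use. For the portal vein, the list of on-device recordings does not provide the second. A team that follows the protocol exactly would reach the analysis with a named outcome and no specified on-device data for it.

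The IVC has data but no test. It comes first in both hypotheses and is recorded at both visits, but the outcome sentence leaves it out and gives no reason. The eligibility criteria exclude patients with an interrupted IVC. There may be other reasons for that exclusion, but it is consistent with the IVC being an intended measurement site. At stake is whether this pilot, meant to prepare for multi-institutional work, has a planned answer for a site that it set out to study.

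**Working it through.** No stated figure needs to be reproduced: the sample size of 15 has no effect size, standard deviation, alpha or power behind it, and the point does not depend on it. The check sets the three parts of the protocol side by side, site by site, for the before/during comparison.

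| Site | In both hypotheses | Pulsed-wave Doppler in both echo lists | Index in the analysis |
|---|---|---|---|
| IVC | yes | yes | **no** |
| Hepatic vein | yes | yes | yes |
| Portal vein | **no** | **no** | yes |
| Pulmonary arteries | yes | yes (RPA, LPA) | yes (pulmonary pulsatility index) |
| Systemic outflow / aortic valve | as cardiac output | yes | yes (VTI) |

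The last two rows assume that the pulmonary index is derived from the RPA/LPA recordings and the VTI from the outflow or neoaortic recordings. The plan does not tie either index to a vessel or view.

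**Portal vein.** Each list has pulsed-wave Doppler at six sites: IVC, hepatic vein, systemic outflow tract, SVC, RPA and LPA. The portal vein is 0 of 6 in each. The subcostal colour Doppler items cover only the IVC and hepatic veins. Of the three pulsatility indices in the analysis (pulmonary, hepatic vein, portal vein), one is in neither hypothesis.

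**IVC.** The site is in 2 of 2 hypotheses and 2 of 2 echo lists, and in 0 of the 4 named outcomes.

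**Number of tests under each repair**, counting one t-test per named outcome:

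- As written: pulmonary, hepatic vein, portal vein, VTI = 4.
- Portal vein deleted and IVC added: 4 − 1 + 1 = 4.
- Portal vein replaced by IVC: 4.
- Portal vein kept and IVC added: 4 + 1 = 5.

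**The case against.** **The clinic echo may already image the portal vein.** The protocol says "Subject then will have his standard clinic echocardiogram" and does not itemise that scan, so a portal vein sample there cannot be ruled out. It would supply only the value before device use. The on-device list is itemised and has no portal vein entry, so the pair would still be incomplete.

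**It may be a slip of the pen.** That is plausible, since putting IVC in place of portal vein would repair both sides at once. The documents cannot confirm it, and a slip in the outcome list still changes what has been prespecified.

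**It is a 15-patient pilot with no power claim or decision rule.** This stands, and it limits how much weight the point carries. It does not remove the mismatch.

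A reader might also infer three stronger things that the documents do not support.

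- *That a later IVC result would be a post hoc choice.* The site is named in advance in both hypotheses and both lists. What is missing is the named index and its test, so such a result would be an unlisted analysis of a prespecified site.
- *That the normal-breathing IVC recording does not exist.* The reader at baseline is "blinded against the condition the patient is in (normal breathing vs breathing through oPEP"), and the 4-week text repeats this, which implies recordings in both states. The contents of the clinic echo are simply not reproduced. That is a general matter affecting hepatic vein, pulmonary and outflow recordings equally, and it is not evidence against the IVC in particular.
- *That the undefined Fontan circuit and the unassigned SVC recording belong to the same error.* No index is named for the Fontan circuit, but the plan does not say which vessel represents it, and a pilot need not attach every recording to an outcome. These are secondary clarifications.

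**Conclusion.** The mismatch is real, and no other part of the document resolves it. One of the four named comparisons (portal vein) has no specified on-device value, and one hypothesised and recorded site (IVC) has no planned comparison. Whether this is one error or two cannot be determined from the text.

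It should be corrected, but it does not block Aim 1: the hepatic vein, pulmonary and aortic valve VTI entries do not have this site mismatch. For the pulmonary and VTI entries, that rests on the assumption about their source recordings given with the table. The conclusions on the portal vein and the IVC need no such assumption, because they follow from which sites are named where.

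**What to change.** In Statistical Considerations, before any data are analysed:

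1. Add an IVC pulsatility index to the outcome sentence, computed from the IVC pulsed-wave Doppler already listed and compared before and during oPEP use.
2. Reconcile the portal vein entry by one of three routes: delete it; replace it with the IVC index, which also completes step 1; or keep it and add portal vein pulsed-wave Doppler to the echo list in both breathing states.

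**Cost.** Deleting or replacing takes a few words and leaves four tests. The on-device IVC recording is already listed at baseline. The value in normal breathing is subject to the same general uncertainty about the clinic echo as every other site.

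Keeping the portal vein costs at least one on-device sample per patient at each visit where the comparison is made, and a second in normal breathing if the clinic echo lacks one. For 15 patients that is 15 × 1 = 15 to 15 × 2 = 30 extra samples per visit. It also raises the count from four t-tests to five, and the protocol names no primary outcome, alpha or multiplicity rule. If this route is chosen, the plan should acknowledge the additional test.

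### For Aim 1, aortic valve VTI is the only output-related variable analysed and heart rate is not analysed, so the planned comparison cannot by itself show whether cardiac output rose

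*Combined protocol and SAP*

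**What the plan says.** Under Study Objectives, the Aim 1 hypothesis is that "oPEP use in Fontan patients will increase flow pulsatility in the inferior vena cava, hepatic veins, Fontan circuit and pulmonary arteries" and, as its last step, "that will ultimately lead to increased cardiac output".

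Statistical Considerations lists pulsatility indices and one output-related variable: "aortic valve VTI will be compared before and at the time of using the oPEP device". The test is given in one sentence: "A repeated t-test will be used for within subject comparison".

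Study Design & Methods identifies the two states through the blinding of the echo reader, who is "blinded against the condition the patient is in (normal breathing vs breathing through oPEP". The device recording always follows the standard echocardiogram. The apical views include "2D of systemic outflow tract", pulse wave Doppler of the outflow tract and continuous wave Doppler of the neoaortic valve. Heart rate, beat interval, stroke volume and a cardiac output calculation appear nowhere in the document.

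**The concern.** VTI is a per-beat quantity. Multiplied by outflow area it gives stroke volume, and it becomes output per minute only after multiplication by heart rate. The intervention is itself a change in breathing pattern, and the device state always comes second in the session. The documents therefore give no ground for taking heart rate to be the same in both states, although they do not show that it differs either.

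If it differs systematically, the paired test on VTI answers a stroke-volume question and leaves the last step of the Aim 1 hypothesis open. A rise in VTI could go with unchanged or lower output, and a flat VTI could hide a rise. Heart-rate variation that averages to zero across patients would, to first order, add noise but no bias. This matters because the Scientific Background presents the study as groundwork for multi-institutional research, where a VTI result could be carried forward as an output signal.

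**Working it through.** **The plan's own figure.** The sample size is 15, justified only by the study being a pilot. It cannot be reproduced, because no alpha, sidedness, power, effect size or SD is given. For context, at an assumed two-sided alpha of 0.05, 15 pairs give 80% power for a standardised paired difference of 0.78 and 90% power for 0.90. For the output question, those figures describe VTI and not output.

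**Inputs.** From the documents: n = 15, a within-patient t-test, and VTI as the only output-related variable. All percentage changes, SDs and correlations below are assumptions.

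**1. Identity.** Output = VTI × area × heart rate. With area fixed within a patient:

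relative change in output = (1 + change in VTI) × (1 + change in heart rate) − 1.

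**2. Break-even heart-rate change** = 1/(1 + change in VTI) − 1.

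- VTI +5%: 1/1.05 − 1 = −4.8%
- VTI +10%: 1/1.10 − 1 = −9.1%
- VTI −5%: 1/0.95 − 1 = +5.3%

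With VTI up 10%, heart-rate changes of −15%, −10%, −5%, 0% and +10% give output changes of −6.5%, −1.0%, +4.5%, +10.0% and +21.0%. With VTI flat, output changes by exactly the heart-rate change.

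**3. Scale against random error.** The 95% half-width for a mean paired change is t(0.975, 14 df)/√15 × SD = 2.145/3.873 × SD = 0.554 × SD. For a VTI-change SD of 5%, 10% or 15% this is 2.8, 5.5 or 8.3 percentage points. A 5% systematic heart-rate shift would thus be larger than, about equal to, or smaller than the random error.

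**4. Precision of the product.** To first order, SD of the relative change in VTI × heart rate = √(SD_VTI² + SD_HR² + 2ρ·SD_VTI·SD_HR). With VTI SD 10% and heart-rate SD 5%:

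- ρ = −0.5: √(100 + 25 − 50) = 8.66, half-width 4.8
- ρ = 0: √(100 + 25) = 11.18, half-width 6.2
- ρ = +0.5: √(100 + 25 + 50) = 13.23, half-width 7.3

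The half-width for VTI alone is 5.5, so the product can be more or less precise.

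**5. Constant-area assumption.** Area varies with diameter squared. A change of 1% or 2% in outflow diameter between states would change area by 1.01² − 1 = 2.0% or 1.02² − 1 = 4.0%.

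**The case against.** The best defence has four parts.

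- *Output is a downstream expectation and not a named endpoint.* The title and most of the analysed variables concern pulsatility, and VTI is a reasonable within-patient surrogate for stroke volume if outflow area is stable. All of this stands. A reader might infer that the plan treats VTI as cardiac output, but it nowhere says so. What remains is that output closes the Aim 1 hypothesis and nothing analysed reaches it.
- *Heart rate is probably recoverable.* The echo lists name views and Doppler modes, not derived quantities; VTI itself is not in them. A reader might infer that heart rate will not be available. The documents do not support that, since beat spacing may be readable from the recorded traces. The gap is an unspecified variable and analysis, not lost data.
- *The harm is conditional.* The documents give no heart-rate shift, direction, VTI effect or SD. The break-even values are arithmetic and do not show that a conclusion would change. This stands, and it limits the claim.
- *Aim 2 fails for another reason.* Its hypothesis, "oPEP use in Fontan patients for a month will increase flow pulsatility", also ends in output, so a reader might blame missing heart rate for both aims. The patient "will have a repeat echocardiogram according to the protocol below" at about 4 weeks, but Statistical Considerations names no baseline-to-4-week test. That is a separate gap, which heart rate would not close.

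**Conclusion.** The point holds for Aim 1. Followed exactly, the plan compares a stroke-volume surrogate between two breathing states and leaves the output step of the hypothesis unanswered. The VTI change does not fix even the sign of the output change unless heart rate and outflow area are constant between states, and the documents do not establish either.

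The size cannot be stated from the documents. The error in output equals whatever systematic heart-rate shift occurs, and at an assumed VTI SD of 10% a 5% shift would be about as large as the 95% half-width. It does not follow that the VTI result will be wrong: VTI remains valid for the stroke-volume question if area is stable. The change is worth making because it is cheap, but confidence that it would alter the conclusion is only moderate.

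**What to change.** In Statistical Considerations, add an exploratory paired comparison of VTI × heart rate between normal and device breathing, using the t-test already planned, and specify that:

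- heart rate is read from the beat spacing of the same Doppler trace and the same beats as the VTI;
- the pulse wave outflow trace is used in both states. The plan does not say whether this or the continuous wave trace at the neoaortic valve supplies the VTI, and the pulse wave trace matches the listed 2D outflow view;
- values are averaged over whole breaths in each state. The number of beats may differ between states if breathing rate differs;
- the result is an estimate with a 95% confidence interval, proportional to output on the stated assumption that outflow area is constant within a patient. The 2D outflow view can be used to check that assumption;
- VTI is reported alongside.

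If this is not wanted, describe VTI only as a stroke-volume surrogate and make no cardiac-output claim. That costs nothing.

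The cost of the main change is a few sentences, one extra reading per trace and one more comparison in 15 patients, with precision that may be somewhat better or worse than for VTI alone. It needs no extra visit or view. It does not supply the missing Aim 2 comparison; if one is added, the same product should be used there.
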